3. TRIAL OBJECTIVES AND OUTCOMES

3.1 Objectives

3.1.1 Primary objective

The primary objectives of the study are to:

- Assess and compare the immune response in two randomised vaccine groups (bivalent Moderna and Novavax) at 28 days post-vaccination measured as binding antibodies (IgG ELISA – Wuhan and/or Omicron) who have been boosted at least six months earlier.
- Assess the rate and severity of reactogenicity within one-week post-second booster for the Moderna and Novavax groups (Timepoint – daily, for seven days post-vaccination).

3.1.2 Secondary objectives

The secondary objectives are to:

- Assess and compare the immune response in two randomised vaccine groups (bivalent Moderna and Novavax) at 28 days post-vaccination measured as functional antibodies (sVNT and nAb) and cell-mediated immunity (CMI).
- Assess and compare the immune response in two randomised vaccine groups (bivalent Moderna and Novavax) at 6, 12, 18, 24 and 30-months post-vaccination measured as binding antibodies (IgG ELISA), functional antibodies (sVNT and nAb), and CMI.
- To describe binding and functional antibodies in the control group compared with the two vaccine groups (bivalent Moderna and Novavax) at baseline, 6, 12, 18, 24 and 30-months.
- To assess whether a fourth COVID-19 vaccine dose provides an immunological benefit over a third dose by comparing CMI at 6, 12, 18, 24 and 30-months in the control group compared with the two vaccine groups (bivalent Moderna and Novavax).
- To evaluate the safety of fourth booster dose regimens.

3.1.3 Exploratory objectives

- To describe the number and severity of breakthrough cases in the control group compared with the two vaccine groups (bivalent Moderna and Novavax) to 30 months post-vaccination.
- To correlate virological markers (viral load and viral genome characteristics) and immunological markers (humoral antibody, CMI) among mild and severe breakthrough cases to 30 months post-vaccination.

3.2 Outcomes

3.2.1 Primary outcomes

Immune response

Binding antibodies – These will be evaluated using the commercial Euroimmun S1 IgG ELISA (Wuhan and Omicron [once available]) on serum collected at seven timepoints (baseline, 28 days, 6 months, 12 months, 18 months, 24 months and 30 months) for the two vaccine groups and six timepoints (baseline, 6 months, 12 months, 18 months, 24 months and 30 months) for the control group. Assays will be completed within 4 weeks of sample collection for the day 28 visit.

Reactogenicity

Reactogenicity for vaccine groups (A&B) will be measured using the accepted standardised method to evaluate systemic and local side effects following vaccination using a structured questionnaire for seven days post-vaccination, as outlined in Table 1 below.

Table 1. Grading system for evaluating systemic and local side effects following vaccination (15, 16).

Local Reaction to Injectable Products^a								
	Mild (Grade 1)	Moderate (Grade 2)	Severe (Grade 3)	Potentially Life Threatening (Grade 4)				
Pain	Does not interfere with activity	Repeated use of nonnarcotic pain reliever >24 hours or interferes with activity	Any use of narcotic pain relief or prevention of daily activity	ER visit or hospitalization				
Tenderness	Mild discomfort to touch	Discomfort with movement	Significant discomfort at rest	ER visit or hospitalization				
Erythema/ redness ^b	2.5 – 5 cm	5.1 – 10 cm	>10 cm	Necrosis or exfoliative dermatitis				
Swelling ^c	2.5 – 5 cm and does not interfere with activity	5.1 – 10 cm or interferes with activity	>10 cm or prevents daily activity	Necrosis				
Hardness ^c	2.5 – 5 cm and does not interfere with activity	5.1 – 10 cm or interferes with activity	>10 cm or prevents daily activity	Necrosis				
Axillary lymphadenopathy	Does not interfere with activity	Repeated use of nonnarcotic pain reliever >24 hours or interferes with activity	Any use of narcotic pain relief or prevention daily activity	ER visit or hospitalization				
Warmth (usually reported with redness)	Absence		Presence					
Itch	Absence		Presence					
^a Grade 0 will be recorded for parameters if specific symptoms are absent.								
^b The measurement should be recorded as a continuous variable in addition to grading the measured local reaction at the greatest single diameter.								
^c Hardness and swelling should be evaluated and graded using the functional scale as well as the actual measurement.								
Systemic (General)^a								
	Mild (Grade 1)	Moderate (Grade 2)	Severe (Grade 3)	Potentially Life Threatening (Grade 4)				

Fever (°C): Oral or axillary temperature	38.0 – 38.4	38.5 – 38.9	39.0 – 40	>40
Nausea	No interference with activity	Some interference with activity	Prevents daily activity	ER visit or hospitalization
Vomiting	No interference with activity or 1 – 2 episodes/24 hours	Some interference with activity or >2 episodes/24 hours	Prevents daily activity, or requires outpatient IV hydration	ER visit or hospitalization for hypotensive shock
Diarrhoea	No interference with activity	Some interference with activity	Prevents daily activity, or requires outpatient IV hydration	ER visit or hospitalization for hypotensive shock
Headache	No interference with activity	Repeated use of nonnarcotic pain reliever >24 hours or some interference with activity	Significant; any use of narcotic pain relief or prevention of daily activity	ER visit or hospitalization
Fatigue/Malaise	No interference with activity	Some interference with activity	Significant; prevents daily activity	ER visit or hospitalization
Myalgia (muscle pain)	No interference with activity	Some interference with activity	Significant; prevents daily activity	ER visit or hospitalization
Arthralgia (joint pain)	No interference with activity	Some interference with activity	Significant; prevents daily activity	ER visit or hospitalization

^a Grade 0 will be recorded for parameters if specific symptoms are absent, or the temperature is <38 °C. In addition, appearance of the following potential signs of myocarditis/pericarditis will prompt referral for cardiology evaluation: Chest pain, dyspnoea, painful breathing, palpitations, or syncope.
				

3.2.2 Secondary outcomes

Immunogenicity

- *Functional antibody* – All samples will be assayed using the GenScript cPass SARS-CoV-2 Neutralization Antibody detection kit for WT and Omicron variant RBD antigen or other key newly emerging variants. Samples will be tested on serum collected at seven timepoints (baseline, 28 days, 6 months, 12 months, 18 months, 24 months and 30 months) for the two vaccine groups and six timepoints for the control group.

- *Neutralizing antibody* - A fraction of samples (20%) will be assessed using a SARS-CoV-2 assay at the PDI, Melbourne up to 12 months. Testing will be at the same time points as for binding antibodies for Wuhan strain and two Variants of Concern (VoC), including Omicron or other key newly emerging variants.
- *Cellular immunity* - Cellular immunity will be assessed on 50% of participants per group of samples collected at seven timepoints for the two vaccine groups and six timepoints for the control group as follows:
 - o *QuantiFERON Human IFN-γ SARS-CoV-2* (Qiagen) will be performed using heparinised whole blood (Wuhan), only up to 12 months.
 - o Peripheral blood mononuclear cells (PBMCs) will be isolated by density gradient centrifugation within 12 hours of collection and stored in liquid nitrogen at MCRI for all samples up to 30 months. Assays will include IFN-γ Elispot, intracellular cytokine assays (flow cytometry) and multiplex cytokine assays (Wuhan and Omicron).

Safety

All solicited AEs will be collected for 7 days, all unsolicited AEs will be collected for 28 days, and all medically attended AEs will be collected for 3 months. SAEs will be collected throughout the 12-month follow-up period.

3.2.3 Exploratory outcomes

- At baseline, previous infections (RAT or PCR positive or symptomatic with close contact) and vaccinations will be recorded.
- Breakthrough infections will be recorded and tested for during the study.
- Nasal swabs will be collected from all severe breakthrough cases and a subset of mild cases within three days of illness. A representative sample of positive samples will be processed for viral load and whole genome sequencing of SARS-CoV-2.
- We will explore the differences in viral load and viral genome characteristics and immunological markers among mild and severe breakthrough cases.

4 TRIAL DESIGN

4.1 Study design

This clinical trial will be a blinded, two-arm randomised study to determine the safety, reactogenicity and immunogenicity of a fourth dose of SARS-CoV-2 vaccines in Australia in adults 18 years or older who have received their third dose of COVID-19 vaccine, at least six months previously. A separate non-randomised control arm will be enrolled for comparison. The groups are described below. The trial intervention will be a single booster dose of vaccine: -

Group	Vaccine given
Group A – (Moderna) 225 participants	Bivalent Moderna (mRNA-1273.214) (Ancestral SARS-CoV-2 25 μ g + Omicron Variant (B.1.1.529) 25 μ g). Replaced by Bivalent Moderna (mRNA-1273.222) (Ancestral SARS-CoV-2 25 μ g + Omicron Variant (BA.4-5) 25 μ g) when introduced.
Group B – (Novavax) 225 participants	Novavax (5 μ g of SARS-CoV-2 spike protein adjuvanted with 50 μ g of Matrix-M)
Group C – (Control group) 150 participants	No vaccine given

We will aim to enrol approximately 225 individuals in each vaccine group and 150 individuals in the control group. This will ensure sufficient representation of participants aged < 50 and \geq 50 years receiving the newer Moderna BA.4-5 vaccine.

The participants and those evaluating reactogenicity will be blinded to the vaccine allocation for the first seven days following vaccination until details are entered in the Australian Immunisation Register (AIR). After that, participants will be aware of their investigational product allocation. Immunologists and laboratory staff will remain blinded to the investigational product allocation.

4.2 Justification for dose

The trial will use standard doses of the bivalent Omicron-specific Moderna and Novavax vaccines in line with current TGA recommendations. The trial will transition to newer Omicron-specific vaccines according to availability in Australia.

4.3 Trial population

The trial population will be adults 18 years and older who have been boosted at least six months earlier with a third COVID-19 vaccine dose. There will be no upper age limit for groups A and B. Only those aged \geq 18 - 60 years will be recruited to group C (controls), as this is the target age group for which the need for additional boosters is not well established. Additional booster doses are strongly recommended for individuals 60 years and over. Procedures will be implemented to ensure an even age distribution for Moderna product transition in each vaccine group.

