	
  
 Group	Vaccine given	
   
 Group A – (Moderna) 225 participants	Bivalent Moderna (mRNA-1273.214) (Ancestral SARS-CoV-2 25µg + Omicron Variant (B.1.1.529) 25µg). Replaced by Bivalent Moderna (mRNA-1273.222) (Ancestral SARS-CoV-2 25µg + Omicron Variant (BA.4-5) 25µg) when introduced.	
 
 Group B – (Novavax) 225 participants	Novavax (5µg of SARS-CoV-2 spike protein adjuvanted with 50µg of Matrix-M)	
 
 **Group C – (Control group) 150 participants	No vaccine given	
  
		Group	Vaccine given	Group A – (Moderna) 225 participants	Bivalent Moderna (mRNA-1273.214) (Ancestral SARS-CoV-2 25µg + Omicron Variant (B.1.1.529) 25µg). Replaced by Bivalent Moderna (mRNA-1273.222) (Ancestral SARS-CoV-2 25µg + Omicron Variant (BA.4-5) 25µg) when introduced.	Group B – (Novavax) 225 participants	Novavax (5µg of SARS-CoV-2 spike protein adjuvanted with 50µg of Matrix-M)	**Group C – (Control group) 150 participants	No vaccine given
Group	Vaccine given									
Group A – (Moderna) 225 participants	Bivalent Moderna (mRNA-1273.214) (Ancestral SARS-CoV-2 25µg + Omicron Variant (B.1.1.529) 25µg). Replaced by Bivalent Moderna (mRNA-1273.222) (Ancestral SARS-CoV-2 25µg + Omicron Variant (BA.4-5) 25µg) when introduced.									
Group B – (Novavax) 225 participants	Novavax (5µg of SARS-CoV-2 spike protein adjuvanted with 50µg of Matrix-M)									
**Group C – (Control group) 150 participants	No vaccine given									
	
*Participants and reactogenicity assessors will be blinded for seven days as vaccine details will be uploaded to the Australian Immunisation Register seven days post-vaccination.
 
**Control group will not be randomised and will be recruited into proportional predefined age bands (18-29 years, 30-49 years, 50-59 years).
									
JUSTIFICATION	
 Investigating a fourth dose will allow us to explore whether additional boosters are needed in a setting with high rates of prior infection. We will include a non-randomised control group aged under 60 years who will not receive a fourth dose to investigate whether three doses are adequate for this age group and what additional benefit a fourth dose provides in terms of cellular immunity as a proxy for moderate/severe disease. 									

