	
 At baseline, previous infections (RAT or PCR positive or symptomatic with close contact) and vaccinations will be recorded. Breakthrough infections will be recorded and tested for during the study, until 30 months post-enrolment. Nasal swabs will be collected from all severe breakthrough cases and a subset of mild cases within three days of illness. A representative sample of positive samples will be processed for viral load and whole genome sequencing of SARS-CoV-2. We will explore the differences in viral load and viral genome characteristics and immunological markers among mild and severe breakthrough cases.
TRIAL POPULATION	
Participants will be adults 18 years or older who have received three doses of any COVID-19 vaccine six or more months before the study start for all three groups. There will be no upper age limit for groups A and B. Only those aged 18 to <60 years will be recruited to group C (controls), as knowledge and the benefit of additional boosters for this age group are not well established. Participants will be recruited from the Murdoch Children's Research Institute, the Royal Children's Hospital (RCH), the University of Melbourne, the Peter Doherty Research Institute, and, if necessary, the greater Melbourne area. We will initially target people working in the medical, science, and healthcare fields and then expand to the general population as needed.
 
450 participants will be recruited into either the bivalent Moderna, or Novavax group. 150 participants will be recruited into the control group. There will be a total of 600 participants. Procedures will be implemented to ensure participants of all ages (aged 18 years and above) are included and that there is an equitable age distribution (<50 and ≥50 years) in each vaccine group and for the bivalent Moderna vaccine transition for the randomised controlled trial.

DESCRIPTION OF SITES	
This will predominantly be a single-site study with participants enrolled at RCH. In select cases participants may be enrolled at GP clinics or community centres.

DESCRIPTION OF INTERVENTIONS	
The two interventions to be studied are as follows:

	
Bivalent Moderna (mRNA-1273.214) (Ancestral SARS-CoV-2 25µg + Omicron Variant (B.1.1.529) 25µg).
 
Replaced by Bivalent Moderna (mRNA-1273.222) (Ancestral SARS-CoV-2 25µg + Omicron Variant (BA.4-5) 25µg) when introduced.

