6 RANDOMISATION AND BLINDING

The two vaccine groups will be randomised 1:1 to one of two interventions (bivalent Omicron-specific Moderna and Novavax) stratified by age (<50 and \geq 50 years). An independent statistician from the Melbourne Children's Trial Centre at the Murdoch Children's Research Institute will provide a secure, password-protected web-based randomisation schedule. Blocked randomisation will be used with random blocks of permuted length.

50% of participants from each vaccine group will be included in the cell-mediated immunity (CMI) subgroup analysis. We will ensure that the age strata (<50 and \geq 50 years) are equally represented in the CMI vaccine groups. As only 10-20 CMI samples can be processed per day, we will recruit the first 10-20 participants per day to participate in this substudy.

The control group will not be randomised and will be recruited from participants <60 years of age who indicate that they are not planning to receive a fourth vaccine dose at the time of recruitment. Controls will be recruited into proportional predefined age bands (18-29 years, 30-49 years, 50-59 years).

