8 ANALYSIS OF THE SECONDARY OUTCOMES

8.1 ANALYSIS OF SECONDARY IMMUNOLOGICAL ENDPOINTS

Table 8 lists the secondary immunological endpoints, including the timepoint measured, population measure, groups being compared and the measure of association between groups. Note there may be additional secondary immunological outcome variables (e.g. relating to new variants of concern) that become available after this SAP is written. These additional variables will be analysed in the same way as other secondary immunological variables listed in Table 8, with analysis dependent on the distribution (e.g. whether symmetrical).

Table 8. Secondary immunological endpoints

Outcome	Population measure	Measure of association	Timepoint	Comparisons
Binding antibody				
Binding antibody (IgG) (Wuhan) BAU/ml	GM (95% CI)	GMR (95% CI)	Month-6	Group A vs B, Group A vs control, Group B vs control
			Month-12	Group A vs B, Group A vs control, Group B vs control
			Month-18	Group A vs B, Group A vs control, Group B vs control
			Month-24	Group A vs B, Group A vs control, Group B vs control
			Month-30	Group A vs B, Group A vs control, Group B vs control
Binding antibody (IgG) (Omicron BA.1), RU/ml	GM (95% CI)	GMR (95% CI)	Day-28	Group A vs B
			Month-6	Group A vs B, Group A vs control, Group B vs control
			Month-12	Group A vs B, Group A vs control, Group B vs control
			Month-18	Group A vs B, Group A vs control, Group B vs control
			Month-24	Group A vs B, Group A vs control, Group B vs control
			Month-30	Group A vs B, Group A vs control, Group B vs control
Binding antibody (IgG) (Omicron BA.4/5), EU/ml	GM (95% CI)	GMR (95% CI)	Day-28	Group A vs B
			Month-6	Group A vs B, Group A vs control, Group B vs control
			Month-12	Group A vs B, Group A vs control, Group B vs control
			Month-18	Group A vs B, Group A vs control, Group B vs control
			Month-24	Group A vs B, Group A vs control, Group B vs control
			Month-30	Group A vs B, Group A vs control, Group B vs control
Binding antibody (IgG) (Omicron JN.1), EU/ml	GM (95% CI)	GMR (95% CI)	Day-28	Group A vs B
			Month-6	Group A vs B, Group A vs control, Group B vs control
			Month-12	Group A vs B, Group A vs control, Group B vs control
			Month-18	Group A vs B, Group A vs control, Group B vs control
			Month-24	Group A vs B, Group A vs control, Group B vs control
			Month-30	Group A vs B, Group A vs control, Group B vs control
Functional antibody				
Functional antibody sVNT (Wuhan), U/ml	GM (95% CI)	GMR (95% CI)	Day-28	Group A vs B

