9.5 SUBGROUP ANALYSES AND TESTS FOR INTERACTION

Analyses for all endpoints will be conducted amongst all strata combined. Primary analyses will combine data from participants receiving the Moderna BA.1 and Moderna BA.4/5 vaccines. Subgroup analyses stratified by the age strata (<50 and ≥50 years) will also be conducted for the immunological endpoints and breakthrough infection secondary endpoints. Subgroup analyses will also be performed by Moderna vaccine timing (Moderna BA.1 period vs Moderna BA.4/5 period) for immunological endpoints. Tests of interaction will be done by fitting a model with an interaction parameter between study arm and the age strata.

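### Controls must be under 60 but the vaccine arms have no age ceiling, and the planned vaccine-versus-control comparisons are not limited to the ages that overlap

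*Protocol*

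**What the plan says.** **Who is enrolled.** Protocol 4.3 states, of the vaccine arms, "There will be no upper age limit for groups A and B". Protocol section 6 says the control group "will be recruited from participants <60 years of age who indicate that they are not planning to receive a fourth vaccine dose", and its oldest recruitment band is 50-59. Protocol 4.3 adds: "Additional booster doses are strongly recommended for individuals 60 years and over". The allocation tables (Protocol 6.1, SAP Table 1) plan 150 participants under 50 and 75 aged ≥50 in each vaccine arm, and 150 controls. Neither the number of vaccinees aged 60 or over nor the number of controls per band is given.

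**What the control arm is for.** The synopsis justifies Group C, which is not randomised, in these words: "control group aged under 60 years who will not receive a fourth dose to investigate whether three doses are adequate for this age group".

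**What is compared.** From Month 6, SAP Table 8 lists "Group A vs B, Group A vs control, Group B vs control". This runs to Month 30 for binding and functional antibody and to Month 12 for neutralising antibody and IFN-γ. SAP Tables 12 and 13 tabulate breakthrough incidence risk for all three groups. SAP 9.5 pools the age strata for every endpoint and then says "Subgroup analyses stratified by the age strata (<50 and ≥50 years) will also be conducted for the immunological endpoints"; it adds the breakthrough endpoints to the same subgroup split.

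**How age is handled.** Protocol 11.3.2, which covers vaccine versus control, says only that age will be accounted for. The SAP's later-visit model (Table 10) adjusts for the randomisation age group, primary series, first booster and baseline level. Its estimand and study arms, however, name only the two vaccine groups.

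**The concern.** Neither document limits the vaccine arms to under 60 when they are set against Group C. Vaccinees aged 60 or over therefore enter a comparison in which nobody of their age went without a fourth dose. Any effect of being over 60 on antibody level, waning, exposure to infection or uptake of further doses becomes mixed with the effect of the fourth dose.

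Extra doses matter in particular. The main later-visit analyses ignore whether a self-initiated fifth dose was taken, and the protocol itself notes that boosters are strongly recommended from age 60.

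The one age term in the SAP's models is <50 versus ≥50. Among controls, ≥50 means 50-59; among vaccinees it is open-ended. Carried over to the control comparisons, that term would treat the two as the same stratum, and the ≥50 subgroup would make the same comparison directly. The result would not answer the under-60 question for which the control arm was set up.

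**Working it through.** **Step 1: the plan's own figure.** Protocol 11.1 assumes a coefficient of variation of 1.15, a GMR of 1.4, two-sided 0.05 and 90% power.
- Log SD = √ln(1 + 1.15²) = 0.918; ln 1.4 = 0.336.
- n = 2(1.960 + 1.282)² × 0.918² / 0.336² ≈ 157 per arm, in line with the stated 160. Then 160/0.8 = 200, as stated.

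This figure covers A versus B. Neither document gives a sample size or power for vaccine versus control.

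**Step 2: distortion if the <50/≥50 term is used.** Let s be the share of ≥50 vaccinees who are 60 or over, r the geometric mean ratio of 60+ to 50-59, and w the weight of the ≥50 stratum in the pooled estimate.
- ≥50 subgroup: the GMR is multiplied by exp(s ln r).
- Pooled: the GMR is multiplied by exp(w s ln r), with stratum weights proportional to n_v n_c/(n_v + n_c).

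Assumptions, none of them in the documents: s = 0.3 to 0.7 (22.5 to 52.5 people, or 10% to 23% of an arm of 225); r = 0.70 to 0.85; 25 to 50 controls aged 50-59.

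Weights:
- 25 controls aged 50-59: older stratum 75×25/100 = 18.75; younger 150×125/275 = 68.18; w = 0.22.
- 50 controls aged 50-59: older stratum 75×50/125 = 30; younger 150×100/250 = 60; w = 0.33.

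| Case | ≥50 subgroup | Pooled |
|---|---|---|
| s = 0.3, r = 0.85, w = 0.22 | × 0.95 | × 0.99 |
| s = 0.5, r = 0.80, w = 0.33 | × 0.89 | × 0.96 |
| s = 0.7, r = 0.70, w = 0.33 | × 0.78 | × 0.92 |

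Simulating 4,000 trials under the middle case gave a pooled factor of 0.967, against 0.963 from the formula. Wider assumptions (s = 0.25 to 1, r = 0.7 to 0.9, 30 to 75 controls aged 50-59) give 0.70 to 0.97 in the subgroup and 0.86 to 0.99 pooled. Higher fifth-dose uptake at 60+ would push the other way.

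**Step 3: scale against sampling error.** With 225 versus 150 and log SD 0.918, the standard error is 0.918 × √(1/225 + 1/150) = 0.097. The largest pooled shift in the table, ln 0.92 = −0.083, is below one standard error. In the ≥50 subgroup with 75 versus 50, the standard error is 0.918 × √(1/75 + 1/50) = 0.168. The largest shift there, 0.7 × ln 0.70 = −0.250, is about 1.5 standard errors.

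**Step 4: cost of restricting to under 60.** Power for a GMR of 1.4 against 150 controls, before adjustment, with the coefficient of variation assumed to hold at later visits:

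| Share of ≥50 stratum aged 60+ | Vaccinees kept | Power, no loss | Power, 20% loss |
|---|---|---|---|
| Unrestricted | 225 | 93.5% | 87.5% |
| 25% | 206 | 92.7% | 86.3% |
| 50% | 188 | 91.7% | 84.9% |
| 100% | 150 | 88.8% | 81.0% |

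For the cellular subset (112 versus 75), if the same coefficient of variation applied, power with 20% loss would go from 59.4% to 56.2% with half of the older stratum removed and to 51.9% with all of it removed.

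**The case against.** The strongest answer has several parts.

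- **The groups share the range 18 to 59.** At least 150 of 225 per vaccine arm lie wholly within it. A reader might infer that the populations do not overlap in age; that is wrong. The gap is at the top only.
- **The SAP does not prescribe the <50/≥50 term for the control comparisons.** Table 10 is written for A versus B, and the protocol leaves the form of age adjustment open. A reader might infer that an inadequate model has been specified. The documents show instead that no model has been specified; carrying Table 10 over is only the natural reading. This changes the charge but leaves the gap. Continuous age without restriction would still extrapolate above 59.
- **An age-matched contrast is already planned.** The <50 subgroup in SAP 9.5 has full overlap. That stands, but it drops the 50-59 controls and does not repair the pooled or ≥50 results.
- **Much of this is descriptive.** The breakthrough endpoints are exploratory and have no regression, so there is no age term to replace. The antibody objective against control is also descriptive; only the cellular objective asks whether the fourth dose gives a benefit. That limits the consequences, although Table 8 still reports ratios with confidence intervals.
- **Baseline adjustment may absorb part of an age effect.** If so, r should be read as the ratio remaining after that adjustment. It would not deal with age differences in waning, exposure or extra doses.
- **The size rests on assumed inputs, and the pooled effect is small.** Both are true.

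**Conclusion.** The point holds as an avoidable mismatch in secondary and exploratory comparisons. Vaccinees aged 60 or over have no control counterpart, nothing in the plan removes them, and the stated question concerns people under 60. If the <50/≥50 term is carried over, it cannot correct this, and the ≥50 subgroup is the most exposed result.

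The documents do not fix the size or the sign. The factors of 0.78 to 0.95 (≥50 subgroup) and 0.92 to 0.99 (pooled) depend on the assumed share aged 60+, the assumed geometric mean ratio and the assumed number of controls aged 50-59. The distortion is nil if no vaccinee is 60 or over, or if outcomes do not differ between 50-59 and 60+.

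A reader might also infer that the trial's main result is compromised. It is not: the randomised A versus B comparison, including the primary endpoint, is unaffected, and so is the <50 subgroup. The change is worth making because it is cheap and makes the analysis answer the question the control arm was set up for.

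**What to change.** 1. In SAP Table 8 and section 9.5, restrict every comparison involving Group C to Group A and B participants aged 18-59 at Day 0, and state this as the analysis set for vaccine versus control.
2. State the covariates for those models, with age as a continuous term or in the control recruitment bands (18-29, 30-49, 50-59).
3. Label the older vaccine-versus-control subgroup 50-59.
4. In Tables 12 and 13, give the three-group breakthrough risks for ages 18-59 and report vaccinees aged 60 or over separately.
5. Keep A versus B at all ages.
6. Reconcile Group C's age limit, because the restriction needs one boundary. The synopsis reads 18 to under 60, Protocol 4.3 reads up to 60, and SAP 3.4 reads over 18 to under 60. Some of this may come from how the text was extracted.

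The cost is SAP wording, since age is already collected, and somewhat wider intervals against control. With 20% loss, the GMR detectable at 90% power moves from 1.42 to at most 1.47, and power for 1.4 falls by at most 6.5 points (87.5% to 81.0%). In the cellular subset the fall is at most 7.5 points (59.4% to 51.9%), if the IgG coefficient of variation applies there.
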